Based on the established inclusion and exclusion criteria, the study investigators will enrol patients followed in their own clinic or new patients referred by other ophthalmologists. After learning and asking questions about the risks and benefits of participating in this study, patients will be requested to sign the appropriate information and consent form. They will then have a complete pre-interventional ophthalmologic evaluation including corrected distance visual acuity (CDVA), a complete slit-lamp biomicroscopy examination, an IOP measurement with the Goldmann applanation tonometer, a measurement of the central corneal thickness with a handheld pachymeter (IOPac Advanced, Heidelberg Engineering, Franklin, MA, USA), and a dilated fundus examination with a particular attention to the cup-to-disk ratio (CDR) of the optic nerve.

Population

A total of fifty (50) glaucoma patients will be included in this prospective study. They will be recruited by two (2) glaucoma specialists at the Notre-Dame Hospital department of ophthalmology (University of Montreal Hospital Center, CHUM). Patients will meet the inclusion and exclusion criteria listed below (Tables 1-2). Participants will undergo a micropulse transscleral cyclophotocoagulation (mTSCPC MP3) treatment session in the affected eye.

Table 1: Inclusion criteria
Patients of either sex and any race aged 18 years old and above.
Followed by a glaucoma subspecialist at University of Montreal Hospital Center.
IOP above target and unresponsive to maximal tolerated medical therapy with or without
previous surgical intervention.
a. mild glaucoma: IOP > 18 mmHg
 b. moderate glaucoma: IOP > 15 mmHg
c. advanced glaucoma: IOP > 12 mmHg
Considered poor candidates for additional filtering surgery or implantation of glaucoma
drainage devices.

Table 2: Exclusion criteria

Patients unable to give informed consent.

Patients with significant scleral thinning, defined as thinning of more than one clock hour noticed on scleral transillumination.

Ocular infection or inflammation in the study eye in the 2 months prior to enrolment. Intraocular surgery in the study eye in the 2 months prior to enrolment.

Baseline Parameters

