The following baseline parameters will be recorded for each patient: age, gender, race/ethnicity, type of glaucoma diagnosis, ocular history (previous surgery and laser therapy), preoperative IOP, number of glaucoma medications prior to intervention, preoperative corrected distance visual acuity (CDVA), preoperative cup-to-disc ratio (CDR), pain level (using a verbal analog scale, see Table 3).

Table 3: Verbal analog scale for pain level	
Pain grade	Description of pain during laser, after subconjunctival anesthesia
None	No subjective feeling of pain.
Mild	Pain easily tolerable.
Moderate	Pain tolerable with difficulty.
Severe	Pain intolerable.

Treatment

The intervention will have to take place within thirty days following the screening appointment and will be executed by one of the two glaucoma specialists listed as the investigators of this study. The procedure will be done under local subconjunctival or rarely retrobulbar anesthesia.

All participants will have a treatment session of micropulse trans-scleral cyclophotocoagulation in the affected eye, using the MicroPulse[®] P3 Glaucoma Device (MP3) powered by the CYCLO G6[™] Glaucoma Laser System (Iridex, Mountain View, CA, USA).

Laser settings will be programmed as follows: power—2000mW-2500mW (average 2000mW) of 810nm infrared diode laser set on micropulse delivery mode; micropulse "on" time—0.5ms; micropulse "off" time—1.1ms; and duty cycle (proportion of each cycle during which the laser is on)—31.33 %.

The laser probe will be applied in a continuous sliding or painting motion from 9:30 to 2:30 and from 3:30 to 8:30. The 3 and 9 o'clock positions will be bypassed to avoid damage to ciliary neurovascular structures, as is standard technique with traditional continuous wave TSCPC. The probe will be applied perpendicular to the limbus with the edge directly on the limbus at all times (fiberoptic tip at 3 mm posterior to the limbus).

The laser will be delivered over 360° for 160–320s. Treatment duration will be adjusted based on iris color and glaucoma severity (mild glaucoma: 160s, moderate glaucoma: 240s, advanced glaucoma: 240-320s).

Post-Intervention Follow-Up

The patients will be seen by their attending ophthalmologist one (1) week, one (1) month, three (3) months, six (6) months, twelve (12) months and eighteen (18) months after the intervention. They will be seen more often if any complication occurs, in which case the frequency of their visits will be decided by their glaucoma specialist.

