
The following follow-up parameters will be recorded at each visit: postoperative IOP, number of glaucoma medications, corrected distance visual acuity (CDVA), cup-to-disc ratio (CDR), and presence of complications detected by a complete slit-lamp biomicroscopy examination. The pain level (using a verbal analog scale, see Table 3) will be assessed while performing the laser treatment.

A less than 25% reduction in IOP from baseline after 1 month on two consecutive visits separated by an interval of 1 week will be the basis for a second treatment. The same criteria will apply for third treatment if necessary. Repeat treatments will be done in the same conditions and settings as the primary treatment.

Primary and Secondary Outcomes

The primary outcome measure of success of this study will be defined as an IOP between 6 and 21 mmHg at final follow-up (18 months) with or without IOP lowering medications, at least 25% reduction in IOP at final follow-up compared to baseline, and no need for incisional glaucoma surgery during follow-up period. The need for a repeat micropulse TSCPC will not be considered a failure.

The secondary outcome measure of success will include the number of repeat treatments, the number of IOP lowering medications at 18 months, changes in CDVA (number of lines reduction or improvement from baseline), the progression of CDR compared to baseline, and the frequency of complications associated with the laser therapy (e.g., prolonged AC inflammation [cells 1+ or higher for more than 2 weeks with topical steroid eye drops], sympathetic ophthalmia, chronic hypotony, phthisis bulbi, scleral thinning).

The outcome of the therapy will ultimately be defined in terms of success rate, hypotony rates, response rates (success and hypotony rates considered together) and retreatment rates.

Statistical Analysis

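### The complication outcome is limited to laser-associated events, with no rule or assessor for association, so the reported frequency can only equal or fall below the all-event frequency

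*Combined protocol and SAP*

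**What the plan says.** Primary and Secondary Outcomes lists, among the secondary measures, "the frequency of complications associated with the laser therapy". Five examples follow in an open list. Only prolonged anterior chamber inflammation has a threshold: "cells 1+ or higher for more than 2 weeks with topical steroid eye drops". The other four (sympathetic ophthalmia, chronic hypotony, phthisis bulbi, scleral thinning) have none.

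The recording instruction under Post-Intervention Follow-Up is broader. At each visit the form takes the "presence of complications detected by a complete slit-lamp biomicroscopy examination", with no condition on cause.

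The same outcomes section also lists change in corrected distance visual acuity, progression of the cup-to-disc ratio and hypotony rates. None of these carries attribution wording.

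On who does what, the Treatment section says the laser session "will be executed by one of the two glaucoma specialists listed as the investigators of this study". Post-Intervention Follow-Up says "The patients will be seen by their attending ophthalmologist". Statistical Analysis provides only frequencies and percentages for categorical data.

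**The concern.** Safety is half of the stated purpose, and the Benefits and Risks text already expects a better side-effect profile than the alternatives. In a study where everyone receives the laser, the data cannot show whether an event would have happened without it. Association therefore has to come from opinion or from a prior list of known complications, and the plan regulates neither.

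These eyes may have had previous surgery and may receive up to three laser sessions, so another explanation for an event will often be available. If the reported outcome keeps only associated events, the error runs in one direction, towards a more favourable safety figure. A reader of the results could not tell how many events were set aside unless those were tabulated too.

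**Working it through.** The plan states no complication rate, precision target or sample size calculation, so there is no figure of its own to reproduce. The check is mainly one of wording, followed by simple arithmetic for scale.

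**Step 1: what the phrase can mean.**

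- *Causality filter.* Someone decides, event by event, whether the laser was responsible. The plan gives no criteria, names no assessor and describes no masking or adjudication. Under Confidentiality, only the investigators have access to the data, so no independent person is described as seeing the events.
- *Label for known complications.* The Risks section uses similar wording for a list containing the same five conditions plus reduced visual acuity and pain. On this reading nobody judges cause, but an event outside the recognised set has no stated route into the count. The opening sections call the technique novel and say few studies have described its outcomes, so unexpected events are among those a safety outcome should catch.

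Both readings allow some recorded events to be left out.

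**Step 2: direction.** Let E be the number of patients with any new or worsened study-eye complication and x the number among them with no event counted as associated. The reported number is E − x, with x ≥ 0. So (E − x)/50 ≤ E/50.

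**Step 3: scale.** N = 50 comes from the Population section. Full follow-up is assumed, with one study eye per patient. The shortfall is x/50, or 1/50 = 2 percentage points per excluded patient.

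The event counts below are assumed, because the documents give none. With E = 8:

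- x = 0: 8/50 = 16%
- x = 2: 6/50 = 12%
- x = 4: 4/50 = 8%

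Other assumed counts, with exact (Clopper-Pearson) 95% intervals:

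| Patients counted | Rate | 95% interval |
|---|---|---|
| 10 of 50 | 20% | 10.0% to 33.7% |
| 8 of 50 | 16% | 7.2% to 29.1% |
| 5 of 50 | 10% | 3.3% to 21.8% |
| 1 of 50 | 2% | 0.05% to 10.7% |
| 0 of 50 | 0% | 0% to 7.1% |

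For a rare event, one exclusion turns 2% into 0%. The intervals reflect sampling error in what was counted and do not allow for events left out.

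**Step 4: what is not affected.** Visual acuity, cup-to-disc ratio and hypotony are reported without reference to cause. An acuity loss put down to the underlying glaucoma would still appear in the acuity outcome. The point is confined to the remaining complications.

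**The case against.** The strongest reply is that the plan describes no attribution step. The Purpose section states the safety outcome without a causal qualifier, recording at visits is unconditional, and the similar phrase in the Risks section reads as a category label. Prolonged inflammation is defined by cell grade and duration, with no clause on cause. Because complications are recorded at every visit and data are kept for 10 years, recorded events could be tabulated later. All of this stands and limits the point. It does not remove it, because the outcome to be reported is the restricted one, and the label reading still leaves unlisted events without a route into the count.

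A reader might infer that the operators also do the follow-up and so decide which harms count. The documents do not say this. The laser is assigned to the two investigators and follow-up to the attending ophthalmologist. Recruitment makes overlap likely for some patients, since "the study investigators will enrol patients followed in their own clinic or new patients referred by other ophthalmologists", and after a complication "the frequency of their visits will be decided by their glaucoma specialist". That is still not a statement that operator and examiner are the same person, and the point does not need it. An unspecified association rule is a gap whoever holds the slit lamp.

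It can also be objected that wider reporting is not free, because the plan has no relatedness assessment at present. That is fair, and it is counted in the cost of the fix.

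**Conclusion.** The concern holds in a limited form. The complication outcome is restricted to laser-associated events with no stated rule or assessor, in a single-arm study without described masking or adjudication. The reported frequency can therefore only equal or fall below the all-event frequency. The certain part of the size is 2 percentage points for each patient excluded out of 50. The 16% against 12% to 8% comparison rests on assumed counts and is no evidence that bias will occur or how large it would be.

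Two stronger conclusions should not be drawn. The plan does not leave visual loss unreported, and it does not describe anyone filtering events case by case. This is a weakness in one descriptive secondary outcome and does not touch the primary outcome. It is worth correcting because safety is a main aim and the correction is cheap.

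**What to change.** In Primary and Secondary Outcomes, define the complication outcome as the frequency of all new or worsened study-eye complications recorded at any visit from the first laser session to 18 months, regardless of presumed cause. Show those judged laser-related only as a labelled subset, and state who makes that judgment and by what rule. The headline figure then no longer depends on it.

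The visits and examinations are already planned, and complications are already recorded without a causality condition. The cost is a change of wording, slightly more tabulation and, for the subset, a relatedness judgment that the plan does not now contain. The main downside is a less favourable headline frequency that includes some events unrelated to the laser. The laser-related figure remains available beside it.

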More recently, a micropulse delivery mode of diode laser (Micropulse TSCPC, mTSCPC) has been used to treat glaucoma by ablating the ciliary processes and reduce aqueous humor production with more selective targeting and less collateral damage.¹³ In contrast to conventional laser delivery where a continuous flow of high intensity energy is delivered, micropulse laser application delivers a series of repetitive short pulses of energy with rest periods in between pulses. This allows energy to build up in the targeted pigmented tissues, eventually reaching the coagulative threshold, while the adjacent non-pigmented structures have time to cool off during the off cycle without reaching the point of coagulation.²⁰⁻²⁷

Only a few studies have described the outcomes of this novel glaucoma therapy, showing mTSCPC to have comparable efficacy with fewer side effects when compared with traditional continuous wave mode diode laser delivery.^{13-14,28} This improved side effect profile has the potential to make mTSCPC an earlier therapeutic option instead of reserving it exclusively for end-stage refractory eyes.

Purpose

The goal of this study is to evaluate the efficacy and safety of the novel form of trans-scleral cyclophotocoagulation using micropulse diode laser and trans-pars plana treatment (Micropulse TSCPC, mTSCPC MP3, IRIDEX CYCLO G6[™] Glaucoma Laser System, CA, USA).

The main outcome will be the efficacy of the mTSCPC MP3 evaluated by the short-term and long-term reduction of IOP and number of anti-glaucomatous drops used postoperatively. The other outcomes will be the safety of this device by looking at the possible decrease in corrected distance visual acuity (CDVA), the progression of the optic nerve cupping and the complications.

Study Design

This will be a prospective, interventional and monocentric study based in a university hospital setting.

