Paired 2-tailed Student t-tests will be used to compare changes in IOP, number of glaucoma medications, CDVA and CDR between each time point. For each of these measures, a single factor analysis of variance will be realized. Snellen visual acuities will be converted to logarithm of the minimum angle of resolution (logMAR) values for statistical analysis. Bonferroni correction will be used to control the multiplicity of t-tests. Frequency distribution and percentage will be used for categorical data. Demographic analysis will use Wilcoxon rank-sum test for age and chi-square test for gender. Fisher's exact test will evaluate equivalence of glaucoma types. A level of $p \le 0.05$ will be considered statistically significant. Analysis will be done with the SPSS version 20.0 software (SPSS Inc., Chicago, IL, USA).

Benefits, Risks and Disadvantages

Benefits

Micropulse trans-scleral CPC is thought to be an effective strategy to reduce the intraocular pressure in patients who are poor candidates for additional filtering surgery or implantation of glaucoma drainage devices. This therapy is considered less invasive and associated with fewer side effects than the traditional trans-scleral CPC procedure.

By participating in this study, patients will contribute to the research community in the ophthalmology field. The results already published on the micropulse trans-scleral CPC are encouraging, but additional results regarding the efficacy and safety of this procedure will further support its beneficial use.

Risks

Participants are exposed to all conventional complications that may be associated with CPC: prolonged anterior chamber inflammation, sympathetic ophthalmia, chronic hypotony, phthisis bulbi, scleral thinning, decrease in visual acuity, pain. However, the side effect profile of micropulse CPC is thought to be better than conventional glaucoma surgeries and conventional CPC, which has been used for many years in the treatment of advanced glaucoma. In case of failure of micropulse CPC to control adequately the IOP, there is always a possibility to add topical or systemic medication, or to undergo another surgery if needed.

Disadvantages

The only disadvantage in participating in this study will be to come to the requested follow-up appointments, which do not imply any risky or painful procedure.

Confidentiality

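### CDVA and CDR, named as safety outcomes, are analysed only by tests of no difference, with Bonferroni on the t-tests and no confidence interval planned, so a non-significant result cannot support safety

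*Combined protocol and SAP*

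**What the plan says.** The Purpose section gives efficacy and safety as the goal. On safety it says: "The other outcomes will be the safety of this device by looking at the possible decrease in corrected distance visual acuity (CDVA"), together with progression of optic nerve cupping and complications.

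Primary and Secondary Outcomes lists, among the secondary measures, "changes in CDVA (number of lines reduction or improvement from baseline), the progression of CDR compared to baseline", and the frequency of complications. It sets no threshold for a harmful change in CDVA or CDR.

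The Statistical Analysis section then treats these two safety measures exactly as it treats the efficacy measures:

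- "Paired 2-tailed Student t-tests will be used to compare changes in IOP, number of glaucoma medications, CDVA and CDR between each time point".
- An ANOVA is added on the same four outcomes: "For each of these measures, a single factor analysis of variance will be realized".
- "Bonferroni correction will be used to control the multiplicity of t-tests". The number of tests in the family is not stated.
- A p-value of 0.05 or less "will be considered statistically significant".
- Categorical data get frequencies and percentages.

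No confidence interval, bound or margin is planned for any of these measures.

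**The concern.** A test of no difference can reveal harm, but it cannot show that harm is absent or small. For CDVA and CDR the plan provides only such tests, so a favourable result can take no form other than a lack of significance. That says nothing about how large a loss the data still allow.

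Bonferroni adds to this. It protects against false positive claims, which is what one wants for IOP and medication count. Applied to a harm measure, it raises the bar for declaring harm. The more comparisons in the family, the larger the worsening that can pass as non-significant at a given visit. Choosing fewer contrasts or a less strict correction would lower that bar but leave the main gap, because no estimate with its uncertainty would be reported.

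At stake is the safety half of the stated goal: a relevant mean loss of vision or progression of cupping could be reported only as no significant change.

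**Working it through.** **Inputs from the protocol.** Sample size, from Population: "A total of fifty (50) glaucoma patients will be included in this prospective study". Visits, from Post-Intervention Follow-Up: "one (1) week, one (1) month, three (3) months, six (6) months, twelve (12) months and eighteen (18) months after the intervention". Baseline plus six visits makes 7 time points. The level is 0.05, two-tailed. The plan has no power calculation to reproduce: it gives no effect size, SD, power or dropout for its 50 patients.

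**Assumed, because the protocol is silent.** A true mean worsening of 0.5 SD of the change; 0.1 logMAR per line; an SD of CDVA change of 0.2 to 0.4 logMAR; 40 eyes at 18 months as an example of attrition.

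**Size of the Bonferroni family.** Each measure has 6 contrasts with baseline, or 7 × 6 / 2 = 21 pairs. Over four measures that is 6 × 4 = 24 or 21 × 4 = 84. The wording of the t-test sentence can be read as all pairs.

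**Chance that one contrast misses the harm.** With k tests the per-test level is 0.05/k. The miss rate is the probability that |T| stays below t(1 − 0.05/(2k), n − 1), where T is noncentral t with n − 1 degrees of freedom and noncentrality 0.5√n. This is 3.54 for n = 50 and 3.16 for n = 40.

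| k | per-test level | critical t (n = 50) | missed, n = 50 | missed, n = 40 |
|---|---|---|---|---|
| 1 | 0.05 | 2.01 | 7% | 13% |
| 6 | 0.0083 | 2.75 | 22% | 35% |
| 24 | 0.0021 | 3.25 | 39% | 54% |
| 84 | 0.0006 | 3.67 | 54% | 69% |

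**In lines of vision.** For a true mean loss of 0.1 logMAR at n = 50 and SD 0.2, 0.3 and 0.4, the miss rate is 7%, 36% and 59% uncorrected, and 39%, 80% and 92% with k = 24.

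**What a non-significant result can hide.** With k = 24 the largest non-significant observed mean is 3.25/√50 = 0.46 SD. The 95% confidence interval extends a further 2.01/√50 = 0.28 SD, to 0.74 SD. At SD 0.3 the observed loss can reach 0.46 × 0.3 = 0.14 logMAR (about 1.4 lines), with an upper limit of 0.74 × 0.3 = 0.22 logMAR (about 2.2 lines).

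**Harm present at every visit.** The table covers one contrast. If a 0.5 SD worsening is present at all six visits, simulation at n = 50 gives these chances that all six baseline contrasts miss it, for k = 6, 24 and 84: about 2%, 7% and 16% if changes correlate 0.5 between visits, and about 7%, 18% and 30% if they correlate 0.8.

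**Why the mean alone is not enough.** If 10% of eyes lose three lines and the rest average no change with SD 0.1 to 0.2, the mean loss is 0.1 × 0.3 = 0.03 logMAR. The overall SD is √(SD² + 0.1 × 0.9 × 0.3²) = 0.135 to 0.219. The t-test detects this in only 34% to 16% of trials uncorrected, and 6% to 2% with k = 24. A proportion shows it directly: 5 of 50 eyes is 10%, with an exact 95% interval of 3.3% to 21.8%. Even 0 of 50 leaves an upper limit of 7.1%.

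**The case against.** The strongest reply is that the protocol never says a non-significant result will be taken as safety. That is correct. A reader might infer it because no other criterion is given, but the documents do not state it. The Primary and Secondary Outcomes section ends by defining the outcome of therapy through success, hypotony, response and retreatment rates, and ties no conclusion to a p-value for CDVA or CDR. The gap is a missing estimate, not a stated misuse.

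Nor is the corrected t-test the only analysis. The ANOVA covers the same measures, and since Bonferroni is applied to the t-tests, it would run at 0.05. Lines lost and complication counts are also outcomes. This softens the point without removing it: the ANOVA is another test of no difference, and no interval is planned for the lines or the counts.

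A reader might also take 39% or 54% as the plan's overall chance of missing harm. That is too strong. Those figures apply to one contrast, such as harm first seen at 18 months; persistent harm has six chances to be detected.

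Finally, one might ask for a formal non-inferiority margin. The case against it is sound. With a one-sided 95% bound, a margin of 0.1 logMAR and no true change, 50 eyes would meet the margin in 97%, 75% and 54% of trials at SD 0.2, 0.3 and 0.4. A harmless device could fail about half the time. In the example where 10% of eyes lose three lines, the same rule would be met in roughly 96% to 71% of trials.

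**Conclusion.** The point holds in a limited form. CDVA and CDR are named as safety outcomes and analysed only by tests of no difference. No interval or bound is planned, so a non-significant result cannot support safety, and Bonferroni makes harm harder to declare.

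For a single contrast at n = 50, the correction raises the chance of missing a 0.5 SD worsening from 7% to between 22% and 54%, depending on the family. These figures rest on an assumed effect in SD units and on a family size the plan does not state. In lines of vision the range is wide (7% to 92% for a one-line mean loss, from no correction to 24 tests) because the SD of change is unknown. The need for an interval does not depend on any of these assumptions.

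These are secondary outcomes in a 50-patient single-group study, but safety is half of its stated goal and the correction is cheap.

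**What to change.** In the Statistical Analysis section:

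1. Restrict Bonferroni to the efficacy measures, IOP and number of medications, and state how many tests the family contains.
2. For the change from baseline to 18 months in logMAR CDVA and in CDR, report the mean with a two-sided 95% confidence interval.
3. Report the proportion of eyes losing a pre-specified number of lines, and the proportion progressing by a pre-specified CDR amount, each with an exact 95% interval. The investigators should set both thresholds before analysis.
4. State that a non-significant test will not be read as evidence of safety.

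No formal non-inferiority margin is required.

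The cost is a few sentences, using data already collected. The downside is a somewhat higher chance of a false signal of harm. With no true change, an unadjusted two-tailed test at 0.05 signals worsening falsely 2.5% of the time, so the two 18-month contrasts together give at most 2 × 2.5% = 5%. With a divisor of 24 the figure is at most 2 × 0.05/48 = 0.2%. If all 12 baseline contrasts on the two measures were read as flags, the ceiling would be 12 × 2.5% = 30%, which is a reason to centre the report on 18 months. In a single-group study the intervals also cannot separate harm from the laser from natural progression of the glaucoma, and the report should say so.

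### Visual acuity safety is defined as lines lost or gained per eye but analysed only through mean logMAR, which can miss loss confined to a few eyes.

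*Combined protocol and SAP*

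**What the plan says.** The Purpose section puts vision under safety: "The other outcomes will be the safety of this device by looking at the possible decrease in corrected distance visual acuity (CDVA". Efficacy is the main outcome there, and CDVA comes among the others.

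Primary and Secondary Outcomes lists the matching secondary outcome as "changes in CDVA (number of lines reduction or improvement from baseline". That is a quantity for each eye, with a direction. No number of lines is set as a meaningful loss, and no time point is attached to it.

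Statistical Analysis assigns CDVA these methods:

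- "Paired 2-tailed Student t-tests will be used to compare changes in IOP, number of glaucoma medications, CDVA and CDR between each time point"
- a one-way analysis of variance on the same four measures, which is again a comparison of means
- "Bonferroni correction will be used to control the multiplicity of t-tests"

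The scale is fixed by "Snellen visual acuities will be converted to logarithm of the minimum angle of resolution (logMAR) values for statistical analysis". The number of tests entering the Bonferroni correction is not given.

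The same section also says in general terms that categorical data will be given as frequencies and percentages. It does not name CDVA there, and no CDVA category is defined anywhere.

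**The concern.** The safety question about vision is whether some eyes get worse. A paired t-test and an analysis of variance ask whether the average eye changed. The two answers can differ in three ways:

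- Loss in a few eyes moves the mean only slightly and also inflates its standard error.
- Small gains in other eyes offset the loss in the mean.
- Bonferroni guards against false claims of an effect. Applied to a harm, it makes a true loss harder to flag.

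At stake is how the vision results will be read. A table with a mean change near zero and a non-significant p-value says little about whether several patients lost useful vision. There is no comparison group that might bring a missed loss to light.

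**Working it through.** **Plan's own figure.** There is none to reproduce. The documents give no power, SD or expected change for CDVA, and the sample size is stated without derivation.

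**Inputs from the protocol.**
- Sample size, from Population: "A total of fifty (50) glaucoma patients will be included in this prospective study". One affected eye is treated per patient.
- Two-sided tests at 0.05, from Statistical Analysis.
- Seven time points: baseline plus visits at 1 week and 1, 3, 6, 12 and 18 months, from Post-Intervention Follow-Up.

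**Assumptions not in the protocol.**
- One line is 0.1 logMAR.
- Five of 50 eyes (10%) lose three lines, +0.30 logMAR each.
- The SD of individual change is 0.05 to 0.20 logMAR.

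**Bonferroni levels.** Each follow-up visit against baseline is 6 tests: 0.05/6 = 0.0083. All pairs of seven time points are 7 × 6/2 = 21 tests: 0.05/21 = 0.0024.

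**Fixed cases.** The paired test is t = mean/(SD/√50) on 49 degrees of freedom. For five eyes at +0.30 and no change in the other 45:

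- mean = 5 × 0.30/50 = 0.030
- SD = 0.0909, standard error = 0.0909/7.071 = 0.01286
- t = 0.030/0.01286 = 2.33, p = 0.024

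This passes 0.05 but fails both Bonferroni levels. Now let some of the other eyes gain one line (−0.10):

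| Other eyes gaining one line | Mean change | p |
|---|---|---|
| 0 | +0.030 | 0.024 |
| 3 | +0.024 | 0.083 |
| 5 | +0.020 | 0.16 |
| 10 | +0.010 | 0.51 |
| 15 | (1.50 − 1.50)/50 = 0.000 | 1.00 |

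In every row, five eyes have lost three lines.

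**Power by simulation.** There were 400,000 runs per row. Individual changes are normal in all 50 eyes, with mean +0.30 in five and 0 in the other 45:

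| SD of individual change | Unadjusted 0.05 | 6 tests | 21 tests |
|---|---|---|---|
| 0.05 | 53% | 9% | 1% |
| 0.10 | 29% | 7% | 2% |
| 0.15 | 18% | 4% | 1% |
| 0.20 | 13% | 3% | 1% |

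If the other 45 eyes gain 0.02 logMAR on average, unadjusted power is below 5% at every SD in the table.

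**What a count would show.** Five of 50 is 10.0%, exact (Clopper-Pearson) 95% CI 3.3% to 21.8%. Gains elsewhere cannot cancel it.

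**Noise in the count.** For an eye with no true change, the chance of crossing a two-line cut is P(Z ≥ 0.20/SD): 2% at SD 0.10, 9% at 0.15 and 16% at 0.20. With five truly harmed eyes, the expected number past the two-line cut is 5 × P(Z ≥ −0.10/SD) + 45 × P(Z ≥ 0.20/SD):

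- SD 0.10: 5 × 0.841 + 45 × 0.023 = 5.2 eyes
- SD 0.15: 5 × 0.748 + 45 × 0.091 = 7.8 eyes
- SD 0.20: 5 × 0.691 + 45 × 0.159 = 10.6 eyes

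**The case against.** **The conversion to logMAR is right.** This stands. On the assumed scale, logMAR and lines are the same quantity. A reader might infer that an outcome in lines tested in logMAR is a contradiction. It is not, and lines can be recovered from the same data. What is at issue is the summary.

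**A count may already be intended.** Frequencies and percentages are planned for categorical data. Complication frequency is a secondary outcome with an open list of examples, and the Risks section names reduced acuity among the complications of this type of laser. Together these permit a table of eyes with reduced acuity. They do not commit to one, and nothing says how large a loss would count. A cut chosen after seeing the data would carry less weight.

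**False reassurance is not in the text.** This stands. A reader might infer that the investigators will report a non-significant test as no visual loss, or that the analysis is bound to miss harm. Nothing in the protocol says the first. The second is untrue: with no change in the other 45 eyes, the unadjusted test gives p = 0.024. Serious events such as phthisis and chronic hypotony are to be reported by frequency whatever the mean shows.

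**The figures rest on assumptions.** This also stands. The 10% rate, the three-line loss and the SD are not in the documents, and the case with p = 1.00 uses gains chosen to cancel the loss exactly. That is why a range is shown. After Bonferroni for 6 tests, power stays below 10% at every SD tried, without any offsetting gain.

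**The count is imperfect.** Agreed: it picks up measurement noise and, with a single arm, cannot attribute loss to the laser. The mean has the same attribution problem.

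**Conclusion.** The point holds as a mismatch between a secondary outcome defined per eye and an analysis named only for means. Under the stated assumptions (50 eyes, 0.1 logMAR per line, five eyes losing three lines), the p-value runs from 0.024 to 1.00 depending on what the other eyes do. With no mean change in the other eyes, power is about 53% to 13% unadjusted and 9% to 3% with 6 tests, for SD 0.05 to 0.20.

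CDVA is a named safety outcome but not the study's main outcome. The point therefore calls for an inexpensive improvement and does not undermine the trial. A reader might go further and take two lines as the correct threshold. The documents give no basis for any particular cut.

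**What to change.** In Statistical Analysis, make the main CDVA safety summary the number and percentage of eyes losing, and separately of eyes gaining, at least a stated number of lines from baseline at 18 months. Give exact 95% confidence intervals and show the full distribution of line changes. The investigators should choose and justify the threshold before looking at outcome data, for example two or three lines.

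Keep the mean logMAR change with its confidence interval as description. Do not apply Bonferroni to this safety outcome. State that a non-significant t-test will not be read as absence of visual loss.

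The cost is one extra table, since CDVA is already recorded at every visit, and a threshold to fix in advance. The report should acknowledge two limits: some eyes cross any cut through measurement noise, and without a control arm the count cannot separate laser harm from disease progression.
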